## 6.6 Pre and Post-Intervention Measures

Participants who meet study criteria and who remain interested in participating in the 2 week intervention will be randomized to treatment or sham groups and undergo a baseline/ pre-intervention testing. The pre-intervention measures will be administered by a trained psychometrist or research assistant who will be blinded to group assignment (sham, real NIR stimulation).

The pre-intervention testing will take approximately 3 – 3.5 hours, and will consist of measures of executive function, recent memory, and mood. These same measures will be given after the two-week intervention has completed.

Individuals with Parkinson disease will complete the pre and post intervention visits when they are “off” their typical dopaminergic medications. This is identical to what Parkinson patients are asked to do as part of standard clinical care when seen at the UF Movement Disorders Clinic. To do so, the Parkinson patients will refrain from taking their parkinsonian medications overnight, with no dopa medication after 10:00 PM the night before. The theoretical rationale for evaluating patients when off dopamine medication is to obtain an index of the true status of their disease state.. The remainder of the protocol (i.e., screening, intervention) will be completed when participants are on their normal medications. When tested ‘off medication’, patients may experience increased slowness, tremors and stability. Because of this, they will be closely monitored and provided a wheel chair. If they become too uncomfortable they can take their medication and will be withdrawn from the study.

In previous IRB- approved studies, we have tested Parkinson patients off medication while they completed an array of cognitive, EEG, and other tasks. We have found that the tolerability was quite good and no participants dropped out of the study for the medication issue. In the current study, we are implementing testing ‘off dopa’ medications at the recommendation of the Parkinson Foundation.

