### **Parkinson Disease Group**

- Participants must have a diagnosis of idiopathic Parkinsons disease by a movement disorders specialist based on UK Brain Bank criteria (Hughes et al., 1992a, 1992b).
- No previous history of brain surgery (DBS, pallidotomy, thalamotomy, or fetal cell implants).
- No evidence of dementia based on scores on a cognitive screener (e.g., Dementia Rating Scale-2 (DRS-2) and score on delayed paragraph recall cannot be lower than 1.0 standard deviation of normative values
- May have difficulties with activities of daily living, but this is due to physical symptoms of Parkinson disease and not because of cognitive problems
- Unwillingness to undergo baseline and followup visits when they are 'off' standard dopamine medication
- Inability to undergo a brain scan

Additional exclusion criteria apply to those individuals who participate in the ***optional brain imaging*** study. The brain scan is optional for all participants except those with Parkinson disease. In that case, inability to undergo a brain scan, before and after intervention, is an exclusion. Exclusion criteria for a brain scan include

- Presence of claustrophobia
- Implants such as pacemakers, heart valves, brain aneurysm clips, orthodontics, non-removable body jewelry, or shrapnel containing ferromagnetic metal.

\*\*Note that we are highly experienced in working with older adults who are identified as experiencing current major depression or other psychological disturbances or who perform below cutoff on standard cognitive screening measures. The PI [[name]] is a boarded clinical neuropsychologist who has been working with this clinical population for over 30 years. The clinical Co-Is ([name], [name], [name], [name]) are experienced neurology clinicians, and the doctoral students on this protocol are clinical psychologists in training with experience in diagnosis and treatment of mood and cognitive disorders. Discussions will be held with individuals of concern and recommendations will be made to appropriate health care providers with permission of the participant and in line with standards of care.

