## 7.2.b. Missingness and Intent to Treat.

All data will be checked for missingness, out-of-range values, and distributional form (i.e., normality, homogeneity of variance). Decisions regarding use of parametric vs. nonparametric statistics will be based on the results of those analyses. Standard summary statistics will be provided for pre- and post-stimulation. Intent to treat analysis will be used to reduce selective attrition bias; participants who are unwilling/unable to continue with intervention will be encouraged to attend the post intervention testing, if possible. Thus, statistical analyses will be performed on two data sets: 1) on all subjects who were successfully screened, randomized and able to participate in at least 1 week of the assigned intervention, regardless of study

completion (intention-to-treat analysis); and 2) on subjects who were successfully screened, randomized and able to complete at least 80% of the treatment assignment.

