### **7.3. Statistical Analyses**

Data for each group (Cognitively Normal, MCI, Parkinson) will be analyzed separately. However the same analytic approach will be taken for each, as described below. Some analyses will be truncated for the MCI groups due to the smaller sample size.

*Aim 1:* Aim1 will test the hypothesis that individuals in the active stimulation group will show improved cognitive function compared to the sham group. Separate mixed model ANOVAs (2 [Group: Active Stimulation, Sham stimulation] x 2 [Occasion: Pre-testing, Post-testing]) will be conducted using the executive and Memory outcome variables. When significant, appropriate post-hoc analyses will be conducted. Additional analytic techniques will involve 'change score' analyses, as well as analyses examining predictors of changes (i.e., age, education, gender).

*Aim 2:* Aim 2 will test the hypothesis that individuals in the active stimulation group will show improved emotion/psychological function compared to the sham group. Separate mixed model ANOVAs (2 [Group: Active Stimulation, Sham stimulation] x 2 [Occasion: Pre-testing, Post-testing]) will be conducted using the mood outcome variables (mood modules NIH Toolbox, STAI, POMS, BDI-II). When significant, appropriate post-hoc analyses will be conducted. Additional analytic techniques will involve 'change score' analyses, as well as analyses examining predictors of changes (i.e., age, education, gender).

*Aim 3:* This neuroimaging aim is exploratory and will test the hypothesis NIR intervention will produce pre-post increases in frontal and temporal brain markers of MRS ATP function and pre-post increases in connectivity in frontal and medial temporal lobe mediated resting state brain networks (resting state fMRI). Although this aim will require extensive data reduction, the overall data analytic plan is similar to that of Aims 1 and 2.

*Aim 4:* This is aim is specific to Parkinson disease and will test the hypothesis that active NIR stimulation will result in greater pre-post intervention improvement in motor parameters (UPDRS, fine motor speed, gait, balance) than sham. Separate mixed model ANOVA's will be conducted similar to those described in Aims 1 and 2.

Finally, we plan to examine whether various 'factors' might potentially be moderators or mediators to intervention success. WE plan to examine age, education, gender, health comorbidities, processing speed and mood.

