### **9. Study Time Line Schedule of Activities**

The Schedule of Participant Activities for this study is as follows:

- **Call #1**- Telephone Prescreening to review the study details, and inclusion/exclusions.
- **Informed Consent Process and Screening Visit**- Informed Consent Process begins with the participant per UF, state and federal guidelines. Once the participant has signed the informed consent, complete medical history, inclusion/exclusion criteria, concomitant medications, and cognitive and mood questionnaires will be administered (listed in section C). If participant formally meets study criteria, then he or she is invited to participate in the intervention phase of the study consisting of baseline, NIR stimulation, and post-baseline testing.
- **Baseline Visit** - This assessment involves a series of computer based measures and other questionnaires. This visit may take approximately 3-3.5 hours. If participants undergo MRI, this will take an additional 1.5 hours.
- **NIR Invention (six in lab sessions over two weeks)** - After completing baseline testing, participants will undergo a series of six interventions in the lab over a period of two weeks. The six treatment visits will be scheduled at the baseline visit to ensure availability of the participant. The treatment will be applied over the head and is detailed in section C. During each treatment visit, participants will fill out mood questionnaires such the POMS. .
- **Post-Treatment Visit**- Following the final day of stimulation, the participant will be scheduled for a post-testing assessment of cognitive and emotional function identical to the baseline visit. Participants will also fill out other questionnaires such as the adverse events and placebo control questionnaires.

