For individuals with Parkinson disease, there is an additional potential discomfort. The PD participants may experience some increase in their symptoms (i.e., increased slowness, tremor, rigidity) when they are tested during the "off medication" state. This is similar to what occurs during their routine clinical evaluation at the Movement Disorders Clinic, when they are asked to come to their clinic appointment after being off their Parkinson medication overnight. For our research study, care will be taken to ensure that the Parkinson patients are transported by wheelchair when necessary and that they are accompanied by a member of the study team. They will be told that if they become too uncomfortable, then they should go ahead and take their medication.

It is possible that there are unknown risks for participating in this study. Individuals will be asked about side effects at each visit and encouraged to share information about subjective changes.

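### Withdrawing a treated Parkinson participant from the whole study for taking medication at the post-intervention off visit needlessly ends collection of the follow-up measures still to be done

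*Protocol*

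**What the plan says.** Section 6.6 has Parkinson participants refrain from dopaminergic medication overnight before both the pre- and the post-intervention visit; screening and the intervention take place on normal medication. It gives a reason for off testing (to index the true disease state), warns of slowness, tremor and stability problems, and then states: "If they become too uncomfortable they can take their medication and will be withdrawn from the study". The sentence does not distinguish the two visits, and the withdrawal is from the study, not from the off-state tests. The same section reports that nobody dropped out over medication in the team's earlier off-medication studies.

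Section 12 repeats the permission without mentioning withdrawal: "They will be told that if they become too uncomfortable, then they should go ahead and take their medication".

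Section 7.2.b sets the approach to attrition: "Intent to treat analysis will be used to reduce selective attrition bias", and "participants who are unwilling/unable to continue with intervention will be encouraged to attend the post intervention testing, if possible". Its first analysis set needs at least 1 week of the assigned intervention, whether or not the study is completed. Its second needs at least 80% of the treatment assignment.

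Section 9 and Table 2 provide one post-treatment assessment: "the participant will be scheduled for a post-testing assessment of cognitive and emotional function identical to the baseline visit". For the Parkinson group, section 6.4c adds that "inability to undergo a brain scan, before and after intervention, is an exclusion", and it also lists "Unwillingness to undergo baseline and followup visits when they are" off medication. Aim 4 in section 7.3 tests whether "active NIR stimulation will result in greater pre-post intervention improvement in motor parameters".

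**The concern.** At the post visit the participant has been randomised, has had the assigned real or sham sessions, and has come in to be measured. Section 7.2.b seeks follow-up even from people who gave up the intervention. Section 6.6 ends follow-up for someone who stayed with it and then used a relief that the protocol allows. With only one post-treatment assessment scheduled, what is not collected that day is not collected at all, and no later analysis plan can recover it.

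Much of what remains does not depend on being off medication, notably the adverse-event query and the questionnaire on which arm the participant believes they were in. The trigger is also related to the Aim 4 outcomes: off-state slowness, tremor and instability overlap with the UPDRS, fine motor speed, gait and balance. Losses could therefore be informative and, if the stimulation works, more frequent in the sham arm.

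**Working it through.** The protocol gives no figure on this point to reproduce, and no effect size or SD for the Parkinson group. The check is a comparison of the text, followed by a calculation on assumed values to show scale.

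**1. Who is affected.** A withdrawal at the baseline off visit precedes any stimulation, and that person falls outside the section 7.2.b set, which needs at least 1 week of intervention. The point therefore concerns the post visit only. A participant who completed the sessions meets the conditions of both section 7.2.b sets, so section 6.6 stops data collection on someone whom the analysis section counts.

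**2. What is lost.** From Table 2 and sections 6.6.5 and 6.8, whatever is unfinished at the time of the dose: cognitive tests, mood scales, motor measures, the follow-up Adverse Events Log, the Placebo Control Questionnaire, and the post-intervention scan if still to be done. Scores obtained before the dose are not said to be discarded.

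**3. Share of an arm.** Section 6.2 plans 20 per Parkinson arm, so each case is 1/20 = 5%.

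**4. Size of a possible motor bias (all inputs assumed except n = 20).**
- Baseline off-state score X ~ N(0,1), lower is better.
- Post score Y = m + 0.7X + √(1 − 0.7²)·e, with e ~ N(0,1), m = 0 for sham and m = −0.5 for active (a true benefit of 0.5 SD).
- A participant takes medication when the off-state score exceeds c, set at the 95th, 90th or 80th centile of N(0,1): c = 1.645, 1.282, 0.842.
- Anyone with X > c left at baseline under the same rule, so only X < c is followed.
- Loss at the post visit = P(Y > c | X < c).
- Complete-case difference = E[Y − X | X < c, Y < c] in sham minus the same in active.
- The whole post motor score is taken as lost. Any part obtained before the dose and kept would shrink the shift.

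Numerical integration gives:

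| c | Sham lost | Active lost | Expected cases among 40 | Difference (true 0.5) | Shift |
|---|---|---|---|---|---|
| 1.645 | 3.2% | 0.8% | 20×0.032 + 20×0.008 = 0.8 | 0.477 | 0.023 |
| 1.282 | 5.9% | 1.6% | 20×0.059 + 20×0.016 = 1.5 | 0.461 | 0.039 |
| 0.842 | 10.9% | 3.3% | 20×0.109 + 20×0.033 = 2.8 | 0.435 | 0.065 |

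As a yardstick, ignoring the truncation, the standard error of the difference in change at 20 per arm is √(2(1 − 0.7)) × √(2/20) = 0.775 × 0.316 = 0.245 SD. The shifts run from 0.023/0.245 = 0.09 to 0.065/0.245 = 0.27 of one standard error.

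With m = 0 in both arms the losses are equal and the difference is 0, so this mechanism does not create an effect where none exists.

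**The case against.** The case for leaving the rule alone has several parts.

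*It hardly ever happens.* Section 6.6 reports no earlier dropouts for this reason, section 12 likens off testing to these patients' routine clinic visits, and section 6.4c screens on willingness to attend off visits. This stands. It limits the importance of the point, but it does not supply a reason for withdrawing someone from the whole study.

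*There is no contradiction with section 7.2.b.* A reader might infer that section 6.6 removes the participant from the intention-to-treat set or deletes scores already taken. The text supports neither. The set is defined regardless of completion, and no sentence discards data. The encouragement to attend post testing is also worded for people who stop the intervention, not for medication use. The conflict is with the section's stated aim, not with a specific instruction.

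*Stopping at the dose has a purpose.* This stands too. It keeps each pre-post pair in one medication state, so it would be wrong to say that the rule gains nothing. Post-dose cognitive and mood scores are no more interchangeable with an off-state baseline than motor scores are. But that argues for stopping off-state testing, not for ending the safety query, the blinding questionnaire or the scan.

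*Motor bias is the main problem.* A reader might infer a serious distortion of Aim 4. The working does not show one. Nor can it be said in general whether on-medication motor scores would bring the comparison nearer to the truth or further from it: that depends on the size of the drug's effect, which the protocol does not give.

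*Handling of such scores belongs in an analysis plan.* For the sensitivity analysis this is fair. Whether the data are collected at all is a conduct rule, and this protocol sets it.

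**Conclusion.** The point holds as a modest, cheap improvement. As written, section 6.6 ends follow-up of a treated Parkinson participant at the only post-treatment assessment, when stopping the off-state tests would be enough. The main cost is the uncollected remainder of that visit and any pending scan, at 5% of an arm per case.

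The possible attenuation of a true motor effect is secondary: about 0.02 to 0.06 SD from an assumed 0.5 SD, and nil if there is no effect. Those figures rest on an assumed effect, a correlation of 0.7, a sharp discomfort threshold on the motor score itself, and losses of about 3% to 11% in sham. The protocol supplies none of these, and its own experience suggests losses nearer the low end or below it.

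**What to change.** In section 6.6, for the post-intervention visit, replace the withdrawal clause with wording such as: *off-state testing stops and the time of the dose is recorded; the participant remains in the study; the remaining safety, blinding and questionnaire measures, the remaining cognitive and mood tests, and the scan if not yet done, are completed and flagged as on-medication.*

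Add that scores taken after the dose, whether motor, cognitive or mood, are not pooled with off-state scores in the main pre-post comparison and are used only in a sensitivity analysis, whose detail can go in the analysis plan. Bring section 12 into line so that participants are told the same thing.

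The cost is protocol wording, a dose-time field, one medication-state flag and one sensitivity analysis, with no extra visits or participants. The downside is that a few flagged on-medication scores will need separate handling.

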### 6.6.1 Executive Measures [NIH Examiner, Stroop]

The executive measures include the NIH Examiner, a computerized battery consisting of 9 individual subtasks described below, and a measures of cognitive inhibition (Stroop task). During post-intervention, an executive measure given as part of screening (Trail Making Test) will be repeated.

**6.6.1a Description of the NIH Examiner:** The National Institutes of Health Executive abilities: Methods for Neurobehavioral Evaluation and Research (Kramer et al., 2012). The NIH Examiner is a computer based battery that involves nine tasks of frontal-executive function and takes around 45 minutes to complete. Funding for development of the NIH Examiner was provided by NINDS in 2005 to develop sensitive, domain-specific tasks of fronto-executive function. The NIH Examiner consists of 9 individual tasks that can be combined into three domain specific scores: *Cognitive Control, Working Memory, and Fluency*. An overall *Executive Composite* score can also be computed (Kramer et al., 2014). In the current study, the **dependent variable for the primary aim will be the “executive composite”**

score calculated from the tasks within the NIH Examiner. Described below are each of the 9 tasks of the battery.

1. *Dot Counting (working memory)*: Participants look at a mixed array of green circles, blue circles, and blue squares. They are asked to count all of the blue circles and remember the final total, before counting the blue circles on new displays. The number of new displays increases from two to seven over a total of six experimental trials. The dependent variable is total correct score over trials 1-6, which contributes to the Executive Composite and the Working Memory factor scores.
2. *N-back (working memory)*: Participants view a series of white squares that appear in different locations on a black screen. In the 1-back trials, participants are required to remember the location of squares and compare the location of each new square to the previous square. In the 2- back trials, participants are required to compare each new square location to the location of the square two trials before. The 2-back will only be administered if sufficient performance is reached on the 1-back (computerized adaptive testing). The 1-back consists of 30 trials total while the 2-back consists of 90 trials. Discriminability (d-prime) is calculated as the difference between the z-transforms of the hit rate and the false positive rate. The dependent variables are the 1-back and 2-back d-prime scores and contribute to the Working Memory factor score and the Executive Composite.
3. *Flanker (inhibition)*: In this task, participants view a row of five arrows presented at the center of the screen and then indicate the direction of the center arrow using the arrow keyboard keys. In some sets of trials, all arrows point in the same direction (congruent); in other sets of trials, the center arrow points in the opposite direction of the rest of the arrows (incongruent). Reaction times are typically longer on the incongruent trials. A total of 48 trials are administered. Total accuracy score and reaction time scores on the incongruent trials are calculated and added together to create the total flanker score. The dependent variable is the total flanker score, which contributes to the Executive Composite and the Cognitive Control factor score.
4. *Continuous Performance Test (inhibition)*: Participants are asked to press a button when they see a five-pointed star, and not respond when they see any other shape. A total of 100 trials are presented, 80% consisting of the five-pointed star. The dependent variable is the total number of false alarm errors made on the stimuli. This variable contributes to Executive Composite and Cognitive Control factor scores.
5. *Anti-saccades (inhibition)*: In this task, participants are asked to watch a moving dot on the computer screen and move their eyes upon presentation of a laterally presented stimulus. Some trials involve moving eyes in the direction of the presented stimulus (prosaccade, 10 trials), and some involve moving eyes in the opposite direction (anti-saccade, 40 trials). The dependent variable is the total number of correct anti-saccade trials, which contributes to the Executive Composite and Cognitive Control factor scores.
6. *Set Shifting (set-shifting)*: Participants are required to match a stimulus on the top of the screen to one of two stimuli located in the lower corners of the screen. Stimuli are matched either based on color or shape depending on the cue. There are three tasks: Task A involves matching stimuli based on shape (homogenous; 20 trials), Task B involves matching stimuli based on color (homogenous; 20 trials), and Task C alternates between matching stimuli based on shape and color (heterogeneous; 64 trials; 32 shape, 32 color). Both reaction time score and accuracy scores are calculated across all blocks. These two scores are summed to create the dependent variable, a total set shifting score. This total set shifting score is used to calculate the Executive Composite and the Cognitive Control factor scores.
7. *Phonemic Fluency (fluency)*: In this task, participants are asked to generate as many words that begin with a particular letter of the alphabet. The task is timed for one minute and participants are given two different letters (F and L) for which they must generate words. The dependent variables are the total number of correct words generated on F and L trials, which contribute to the Executive Composite and Fluency Factor scores.
8. *Category Fluency (fluency)*: This task is similar to "phonemic fluency". However, participants are

asked to generate as many words possible that belong to a particular category. This task is timed for one minute and participants are given two categories (animals and vegetables) for which they must name items. The dependent variables are the total number of correct words generated on animal and vegetable trials, which contribute to the Executive Composite and Fluency Factor scores.

9. **Unstructured Task** (planning): In this task, participants are presented with three booklets, each containing five pages of puzzles. Puzzles are cognitively simple but may take anywhere from 4 to 60 seconds to complete, and are associated with a specific point value. Participants are given six minutes to complete puzzles and are required to use judgment and planning skills in order to earn as many points as possible. The dependent variable is the total number of points earned during the 6 minutes. The score on this task is not factored in to the Executive Composite or the factor scores.

**6.6.1b. Description of the Stroop** (Golden version). This version of the Stroop is a standard task given as part of the typical neuropsychological exam and is pre-approved by the IRB. It involves 3 parts: Word Reading, Color Naming, and Color-Word Interference. During Word Reading, a participant reads the words (red, blue, green) typed in black ink on a white page, vertically. Final trial score is total number of words read in 45". During Color Naming, the participant rapidly names the color patches (red, green, blue) that are arrayed on a card. Final trial score is total number of patches accurately identified in 45". During the Color-Word Interference condition, a word (i.e., Red) is printed in color ink that differs in meaning from the meaning of the written word. The participant's task is to name the ink color of the word, and inhibit reading the word. Final trial score is total number of items identified over 45". The **dependent variable** is the cognitive inhibition score, which is based on the Color-Word interference score, taking into account performance on the 2 baseline trials.

